**Table 4 CARIFS Questionnaire Data Recording Time Periods**

Period	Time a
Morning	05.00–10.59
Noon	11.00–14.59
Evening	15.00–18.59
Bedtime	19.00–23.59

a data should not be recorded between 00.00 and 04.59.

In the case where the device was activated after Day 1, the actual day will be used as the assessment day rather than the device-labelled day. In the case where assessments should be recorded twice daily (morning and evening) but are recorded for more than two time periods, only the morning and evening assessments will be presented in summaries over time. In the case where assessments should be recorded once daily but are recorded for more than one time period, a conservative approach will be taken to select the data points to be included in the summaries over time.

In the case where the recorded time of an assessment is outside the period time window for that assessment, the end time of the period should be imputed as the assessment time.

In the case where the assessment time falls into the period between 00.00 and 04.59 (due to technical error) the assessment date will be imputed to the date prior to recorded assessment date and the assessment time will be imputed to the end time of the period time window.

The possible scores for the 18 symptoms specified in the CARIFS questionnaire (see [Appendix 4](#)) are:

- 0 (“No Problem”)
- 1 (“Minor Problem”)
- 2 (“Moderate Problem”)
- 3 (“Major Problem”)
- 4 (“Don’t Know/Not Applicable”)

The imputation method used in the derivation of time to alleviation of influenza signs and symptoms is described below. No further imputation methods will be used.

In all time to event analyses, patients who withdraw prior to event of interest will be censored at the last observation timepoint.

If the number of patients in the ITTi set is small, then listings may be provided.

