### **Time to Alleviation of Influenza Signs and Symptoms**

Time to alleviation of influenza signs and symptoms (TTAS) in hours, will be summarized using descriptive statistics, as well as Kaplan-Meier plots. It is defined as the length of time taken from the start of treatment to the point at which all of the following criteria are met and remain so for at least 21.5 hours:

- A score of 0 (no problem) or 1 (minor problem) for cough and nasal symptoms (items 14 and 15 of the CARIFS questionnaire, see [Appendix 4](#)).
- A “yes” response to the following question on the CARIFS: “Since the last assessment has the subject been able to return to day care/school, or resume his or her normal daily activity in the same way as performed prior to developing the flu?”
- Return to afebrile state (tympanic temperature  $\leq 37.2^{\circ}\text{C}$ ).

If a score of 4 (“Don’t Know/Not Applicable”) occurs at any assessment during the study for items 14 or 15, the assessment will not be included in the calculation of the alleviation of symptoms because the assessment was unobservable.

Patients with symptom scores  $\leq 1$  for both items 14 and 15, as well as tympanic temperature  $\leq 37.2^{\circ}\text{C}$  and a “yes” response to the question “Since the last assessment has the subject been able to return to day care/school, or resume his or her normal daily activity in the same way as performed prior to developing the flu?” simultaneously at baseline will be excluded from the analysis.

Patients who do not experience alleviation of symptoms prior to completion or withdrawal from study will be censored at the last observation time point.

Baseline is defined as the first CARIFS assessment on Day 1 after the start of treatment. Patients who do not have a CARIFS assessment on Day 1 after the start of treatment will have their baseline CARIFS assessment set to missing.

The number of patients with completed CARIFS as well as the number with missing CARIFS per assessment will be presented for the ITT and ITTi sets. Additionally, the number and percentage of those with “Don’t Know/ Not Applicable” per question per assessment will be presented for the ITT and ITTi sets.

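### The SAP rule for diary entries stamped 00.00–04.59 ignores the period label, so a morning entry can be moved 13 to 18 hours back, ahead of the previous evening's entry (low priority)

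*SAP*

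**What the plan says.** SAP 4.3.1, Table 4, sets four recording periods: morning 05.00–10.59, noon 11.00–14.59, evening 15.00–18.59 and bedtime 19.00–23.59. Its footnote adds that "data should not be recorded between 00.00 and 04.59".

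Two rules below the table deal with entries at the wrong time:

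- **General out-of-window rule.** If the recorded time lies outside the window for that assessment, "the end time of the period should be imputed as the assessment time". No change of date is mentioned.
- **Night rule.** This covers times in 00.00–04.59, which the SAP attributes to technical error. The instruction is that "the assessment date will be imputed to the date prior to recorded assessment date and the assessment time will be imputed"; the value used for the time is the close of the period window. No period label is exempted.

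The section also states: "No further imputation methods will be used". CARIFS is scheduled morning and evening on Days 1 to 9 (Protocol 3.1 and Appendix 1; SAP Appendix 2), so no bedtime CARIFS entry is planned. For time to alleviation of signs and symptoms (TTAS), "Baseline is defined as the first CARIFS assessment on Day 1 after the start of treatment".

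**The concern.** A previous-date shift makes sense when the form belongs to the day before, such as an evening form finished after midnight. A morning form belongs to the day on which it is stamped. If it is stamped shortly before 05.00 it is a few minutes early for its own window, yet the night rule places it on the day before.

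TTAS, duration of symptoms and time to return to normal health and activity all depend on the order of entries and on a state lasting at least 21.5 hours. An entry filed before the previous evening's entry can hide a relapse, create one, or change the start of a qualifying run. A Day 2 morning entry would move to Day 1 and could land before dosing or take the place of the baseline.

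**Working it through.** The plan gives no figure of its own to reproduce. The check is clock arithmetic on the Table 4 windows, followed by the 21.5-hour rule applied to illustrative diaries.

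**Step 1: size of the shift.** The night rule is read as using the end of the entry's own labelled period, because the preceding sentence ties the window to that assessment. Backward shift = (stamped time + 24 h) − end of labelled period.

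| Label | Period end | Stamped 00.00 | Stamped 04.59 |
|---|---|---|---|
| Morning | 10.59 | 13 h 01 min | 18 h 00 min |
| Noon | 14.59 | 9 h 01 min | 14 h 00 min |
| Evening | 18.59 | 5 h 01 min | 10 h 00 min |
| Bedtime | 23.59 | 0 h 01 min | 5 h 00 min |

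A morning entry stamped 04.30–04.59 moves 17 h 31 min to 18 h 00 min.

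**Step 2: order.** The new time, 10.59 on the previous day, is before that day's evening window opens at 15.00. An evening entry recorded outside its window would itself be set to 18.59. The re-dated morning entry therefore precedes the previous day's evening entry, and that day has two morning entries.

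**Step 3: effect on the event time.** The diaries below are assumed, not taken from the documents. The stamp is taken as correct, and usual entries are at 08.00 and 17.00.

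- *Example 1.* Ill before Day 3; well Day 3 08.00 and 17.00; ill Day 4 04.45; well from Day 4 17.00 to Day 5 17.00. Day 3 08.00 to Day 4 04.45 is 20.75 h, short of 21.5 h, so the event is Day 4 17.00. Under the night rule the ill entry becomes Day 3 10.59. The run then starts at Day 3 17.00 and reaches Day 4 17.00 (24 h), so the event is Day 3 17.00: **24 h too early**.
- *Example 2.* Ill through Day 3 17.00; well from Day 4 04.45 onward. The event is Day 4 04.45. Under the night rule that well entry becomes Day 3 10.59 and is followed by the ill entry at 17.00. The event is then Day 4 17.00: 17.00 − 04.45 = **12.25 h too late**.

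Further patterns, with dosing assumed at Day 1 12.00 and the Day 4 morning entry stamped 04.50:

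| Pattern | TTAS, recorded time | TTAS, night rule |
|---|---|---|
| Well from Day 3 08.00 onward | 44.0 h | 44.0 h |
| Well from Day 3 17.00 onward | 53.0 h | 47.0 h |
| Well from Day 2 17.00, ill only at Day 4 04.50 | 29.0 h | 53.0 h |
| Well from Day 4 17.00 onward | 77.0 h | 77.0 h |

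**Step 4: Day 1.** A Day 2 morning entry stamped 04.45 becomes Day 1 10.59. If dosing was later than 10.59, the entry falls before dosing. If dosing was before 10.59 and no earlier post-dose Day 1 entry exists, it becomes the baseline, assuming imputed times are used to pick the baseline.

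**Step 5: the overlapping rule.** A morning entry stamped 04.45 also meets the general out-of-window rule, which gives 10.59 on the recorded date. The two rules differ by exactly 24 h.

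**The case against.** The strongest reply is that the problem may never arise. The SAP says entries should not be made in these hours and calls such stamps technical errors. The documents do not say whether the device offers a morning form before 05.00 or how it labels entries. If the clock itself is faulty, the true time is unknown and the 24 h and 12.25 h figures are not demonstrated errors. All of this stands: it limits the weight of the point, and the examples hold only if the stamp is right. It does not explain why a morning label should belong to the previous date.

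The period window might also be read as bedtime for every such entry. The shift would then be at most 5 h and the order would hold. The text does not say this, and no bedtime CARIFS entry is scheduled, so this reading is the weaker one. One may also presume that the specific rule overrides the general one. That is reasonable, but it selects the wrong day for a morning form.

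A reader might infer more than the documents support:

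- *That the rule misdates alleviation whenever it is applied.* It does not. The effect depends on neighbouring entries, can go either way, and is zero in two of the patterns above.
- *That it yields negative times.* For TTAS this would also need no usable Day 1 post-dose entry, because an infant already alleviated at baseline is excluded. The other two endpoints state no such exclusion, but the infant would still have to be recorded as alleviated from the first entry on, and pre-dose entries would have to count.
- *That the shift is large against the 44.6 h median in Protocol 1.2.4.* That study enrolled ages 6 months to under 12 years and its endpoint had no daily-activity criterion. One patient's shift may also leave a Kaplan-Meier median unchanged.

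**Conclusion.** The point holds as a defect in a stated rule, at low priority. As written, a morning-labelled entry stamped 00.00–04.59 moves back 13 h 01 min to 18 h 00 min and ahead of the previous day's evening entry. Any resulting change to TTAS, duration of symptoms or time to normal activity is conditional: none, early or late, with 24 h and 12.25 h as worked cases. The two overlapping rules give answers 24 h apart and neither is given precedence.

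This rests on reading the window as the entry's own labelled period and on taking the stamp as correct. The number of such entries is not known from the documents and may be zero. The endpoints are secondary and descriptive, in a single-arm study of about 30 infants with no hypothesis testing. The adverse event analysis is not affected, and nothing here shows that any reported result would be materially wrong.

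**What to change.** Amend SAP 4.3.1 as follows:

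- Apply the previous-date shift only to entries whose label belongs to the previous day: evening, bedtime and any noon entry.
- For a morning-labelled entry stamped 00.00–04.59, keep the recorded date and impute 05.00, the start of the window. This moves the entry forward by 1 min to 5 h and preserves the order.
- State that this rule takes precedence over the general out-of-window rule.
- State that no imputed time may fall before dosing or before an earlier recorded entry.

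Take the diary dosed at Day 1 12.00 whose first well entry is Day 4 04.50. TTAS is 64.8 h on recorded time, 65.0 h with 05.00 imputed, 71.0 h under the same-date out-of-window rule (10.59) and 77.0 h under the present night rule.

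The cost is a short SAP edit and a small programming change, with no new data. The downside is reliance on the recorded date for the few morning entries that may be affected.

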4.4.3 Prohibited Therapy

The use of the following drugs and over-the-counter drugs with equivalent efficacy are prohibited from Day 1, after administration of study drug, until study completion or early termination:

- Systemic antiviral drugs
- Antipyretics/analgesics except acetaminophen
- Corticosteroids in injection, oral, or inhalation formulation
- Immunosuppressants

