6.1.2 Per Protocol Population

Not applicable.

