**Table 2 Acceptable Time Windows for Parameters other than Data from the Patient Diary and PK Assessments**

Time Point (Scheduled Time point)	Acceptable Time Window
Pre-dose at Visit 1 (Day 1) a	Before dosing on Day 1
Post-dose at Visit 1 (Day 1) a	After dosing on Day 1
Visit 2 (Day 2)	Day 2
Optional Visit 1 (Day 3)	Day 3
Visit 3 (Day 4)	Between Day 4 and Day 5
Visit 4 (Day 6)	Between Day 6 and Day 7
Visit 5 (Day 10)	Between Day 8 and Day 12 as follows: If a patient presents between Day 8 and Day 11 and presents on Day 12 then the visit between Day 8 and Day 11 will be classed as Visit 5 and the Day 12 visit will be classed as Optional Visit 2 If a patient does not present between Day 8 and Day 11 and presents on Day 12 this will be classed as Visit 5
Optional Visit 2 (Day 15)	Between Day 12 and Day 22
Visit 6 (Day 29)	On or after Day 23

a If time is missing for data collected on Visit 1 where this data should be collected at 'v1 screening' or 'v1 post-dose' as per the schedule of activities, then it is defined as 'Pre-dose at Visit 1 (Day 1)' or 'Post-dose at Visit 1 (Day 1)', respectively.

Measurements collected within the acceptable time window for each scheduled assessment time point, including data obtained at the time of withdrawal, will be used for the analyses of all endpoints at each assessment time point. For all patients with multiple values within a visit window, the value obtained closest to the target time point will be used. If two measurements collected with the same time deviation exist before and after the target time point, the measurement obtained before the target time point will be adopted for analysis. The assessment time point having no measurements within the corresponding acceptable time window will be considered as missing.

In the assessment of data from sources other than the patient diary, if there are multiple values which may be adopted for a scheduled assessment time point (even though the above rules have been strictly followed), the measurements at the time point entered in the Case Report Form (CRF) will be adopted.

For summaries of data not collected by visit, such as AEs, medical history and concomitant medications, all data up to the study completion/discontinuation date will be included.

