### **Time to Cessation of Viral Shedding by Virus Titer**

Time to cessation of viral shedding by virus titer is defined as the time, in hours, between the initiation of any study treatment and first time when the influenza virus titer is below the limit of detection ( $0.75 \log_{10} \text{TCID}_{50}/\text{mL}$ ). Patients whose virus titers have not reached the limit by the last observation time point will be treated as censored at that time point. One day is converted into 24 hours.

Patients with a positive virus titer on Day 1 will be included in this analysis.

This endpoint will be summarized using descriptive statistics, as well as Kaplan-Meier plots.

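### The SAP has no rule for infants given another systemic anti-influenza antiviral or withdrawn for worsening influenza; censoring them, or counting recovery on the other drug, favours baloxavir

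*SAP*

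**What the plan says.** Protocol 4.4.3 lists systemic antivirals among the drugs that are "prohibited from Day 1, after administration of study drug, until study completion or early termination". Protocol 4.3.3 names acetaminophen as the only rescue medication. Neither document says how an infant who does receive another antiviral is to be analysed.

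The SAP has only general rules:

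- **All time-to-event endpoints (4.3.1, text after Table 4):** "In all time to event analyses, patients who withdraw prior to event of interest will be censored at the last observation timepoint". The same text adds, beyond the imputation for time to alleviation of signs and symptoms (TTAS): "No further imputation methods will be used".
- **TTAS:** "Patients who do not experience alleviation of symptoms prior to completion or withdrawal from study will be censored at the last observation time point".
- **Viral shedding by titer (4.3.2):** the event is the "first time when the influenza virus titer is below the limit of detection", and "Patients whose virus titers have not reached the limit by the last observation time point will be treated as censored at that time point".
- **By-visit data (4.1, Table 2):** "The assessment time point having no measurements within the corresponding acceptable time window will be considered as missing".

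The two TTAS sensitivity analyses deal with 'don't know' scores and with the daily-activity question, not with other antivirals. The per-protocol population is "Not applicable" (Protocol 6.1.2). Major deviations, withdrawal reasons and concomitant treatments are listed or summarized (SAP 4 and 4.5.1), but none of these changes an estimate.

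**The concern.** Kaplan-Meier censoring assumes that an infant who leaves would have gone on to recover like those still followed. That is hard to defend when the infant leaves because influenza worsened or to be given another drug. Withdrawal for non-compliance is discretionary (Protocol 4.6.2), so the same clinical course can instead lead to an infant who stays in. A later recovery or negative swab is then an event timed from the baloxavir dose, although another antiviral may have produced it. Titers and RNA measured after that drug also enter change from baseline, proportion positive and AUC.

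The direction is the same in both cases, and the infants concerned are those in whom a single dose did least well. With about 30 infants, a few such cases are a visible share of the sample. The study is open-label, so without a rule fixed in advance the handling could be chosen with outcomes in view.

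**Working it through.** The plan has no figure of its own to reproduce: it has no hypothesis test and no formal sample-size calculation. What follows is an illustration.

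**Inputs**
- N = 30 (Protocol 6.2, SAP 2.2).
- Median 44.6 h, from the Japanese paediatric study in Protocol 1.2.4. That endpoint covered cough, nasal symptoms and fever, with no daily-activity criterion, so using it for TTAS is an assumption.
- Exponential recovery (assumption): λ = ln 2 / 44.6 = 0.01554 per hour.
- Diary end at Day 15: 14 × 24 = 336 h.
- Share of infants q given another antiviral, or withdrawn for worsening influenza: 3/30 = 0.10 or 6/30 = 0.20 (assumption; the documents give no rate).
- Illustrative timings (assumption): withdrawal at 36 h, or recovery at 96 h for an infant who stays in.

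**Alleviated by Day 15**, with exp(−336λ) = 0.0054:
- (a) Stays in, recovers at 96 h, counted as an event: 1 − (1 − q) × 0.0054. For q = 0.10 this is 99.5%; for q = 0.20, 99.6%.
- (b) Withdrawn and censored at 36 h. At that time S(36) = q + (1 − q) × exp(−36λ), with exp(−36λ) = 0.5715. This gives 0.1 + 0.9 × 0.5715 = 0.614, and 0.2 + 0.8 × 0.5715 = 0.657. Afterwards S(336) = S(36) × exp(−300λ) = S(36) × 0.0094, about 0.006 in both cases, so 99.4% alleviated.
- (c) Carried event-free to Day 15: (1 − q) × (1 − 0.0054). For q = 0.10 this is 89.5%; for q = 0.20, 79.6%.

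**Median, large-sample**
- (c) t = −ln[(0.5 − q)/(1 − q)] / λ: 0.811/0.01554 = 52.2 h, and 0.981/0.01554 = 63.1 h.
- (b) t = 36 + ln[S(36)/0.5] / λ: 36 + 0.206/0.01554 = 49.3 h, and 36 + 0.273/0.01554 = 53.6 h.
- Differences: 2.9 h (q = 0.10) and 9.5 h (q = 0.20).

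**Simulation at n = 30** (2,000 runs per row; antiviral or withdrawal at the time shown; under (a), recovery after the antiviral is exponential with the same median). The last three columns give the proportion alleviated by 216 h.

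| Infants | Time | Median (a) | (b) | (c) | 216 h (a) | (b) | (c) |
|---|---|---|---|---|---|---|---|
| 3/30 | 24 h | 45.2 | 47.9 | 49.7 | 96% | 96% | 87% |
| 3/30 | 48 h | 49.1 | 49.5 | 49.5 | 96% | 96% | 87% |
| 3/30 | 72 h | 49.0 | 49.0 | 49.0 | 96% | 96% | 87% |
| 6/30 | 24 h | 47.7 | 49.6 | 59.3 | 96% | 96% | 77% |
| 6/30 | 48 h | 55.4 | 56.6 | 59.4 | 96% | 96% | 77% |
| 6/30 | 72 h | 59.2 | 59.2 | 59.2 | 95% | 95% | 77% |

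With censoring at 36 h, the simulated median differs between (b) and (c) by about 0 h for 3 infants and about 6 h for 6. Small-sample results depend on how the median is read when the curve sits at exactly one half. The sampling SD of the median is about 12 to 16 h.

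So the upper part of the curve changes in every row. The median changes only when the antiviral or withdrawal comes early: by at most 49.7 − 45.2 = 4.5 h for 3 infants and 59.3 − 47.7 = 11.6 h for 6.

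**The case against.** The case on the other side has five parts.

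- **Counting outcomes whatever other drug is taken is a recognised strategy.** This stands for infants who stay in, so replacing it as the main analysis would be a trade-off, not a correction. It does not cover withdrawals: censoring does not observe the outcome after the other drug, it assumes recovery like that of the infants still followed.
- **The size rests on assumptions.** This stands. No rate of other antiviral use is given, Protocol 4.1.2 excludes infants expected to need prohibited medication, and the 44.6 h comes from a differently defined endpoint.
- **The planned summaries are Kaplan-Meier plots and medians.** This stands in part. The Day 15 proportion is not a planned statistic, but the plot shows it.
- **Such cases remain visible.** Withdrawal reasons, deviations, concomitant treatments and adverse events are reported, and hospitalization and pneumonia count as complications. A reader should not infer that failures disappear from the report; they are only missing from, or credited in, these estimates.
- **Efficacy is secondary and descriptive.** This stands. No type I error or power is involved.

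A reader might also infer that titers suppressed by another antiviral would leave possible resistance unsequenced. SAP 4.4 does not support that. PA is sequenced in treated infants with evaluable virus at baseline and at the last evaluable timepoint, without reference to Table 6; the Table 6 criteria concern PB1 and PB2 only.

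**Conclusion.** The gap is real and the direction of bias is predictable, but the scope is limited. It covers infants censored on withdrawal for worsening influenza or to receive another antiviral, and infants who stay in and recover or clear virus on one. It would be wrong to infer that every such infant flatters the drug: one who stays in and never alleviates is censored at the last observation, which already keeps the infant event-free. Nor is withdrawal automatic after antiviral use.

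Under 10% to 20% affected and an exponential median of 44.6 h, both assumed, the curve shows about 99% alleviated by Day 15 against 90% or 80%. The median moves by 0 to about 5 h with 3 infants and 0 to about 12 h with 6. It does not move when the antiviral starts after the median, and all these shifts lie within the sampling SD of 12 to 16 h. This is a worthwhile, inexpensive improvement to secondary descriptive analyses. If no such case occurs, nothing changes.

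**What to change.** **SAP 4.3.1.** Add a pre-specified analysis of TTAS and the duration endpoints, shown beside the current rule. Infants who receive another systemic anti-influenza antiviral after dosing and before the event, or who withdraw for worsening influenza or to receive one, are carried event-free to Day 15.

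**SAP 4.3.2.** Add a parallel sensitivity analysis that excludes swabs taken after the first such dose and treats the infant as not having ceased shedding. State how change from baseline and AUC are computed once those swabs are dropped.

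**Both sections.** Report the number of infants affected, separating those who stayed in from those who withdrew. Table 6 needs no change.

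**Cost.** SAP wording and a few flags. Concomitant medications and the primary reason for withdrawal are already recorded on the eCRF (Protocol 4.4 and 4.6.2). The change is analytic only and alters no treatment rule. The downside is a little more programming and, if such cases occur, a somewhat less favourable alternative estimate. An antiviral given as a precaution would also count as a failure in the added analysis, which is a reason to show it beside the current rule and not in its place.
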